12 EVALUATION AND REPORTING OF ADVERSE EVENTS

12.1 Adverse Event Definitions

An AE is defined as any untoward medical occurrence in a subject administered a medicinal product and which does not necessarily have to have a causal relationship with this treatment. AEs occurring after the initiation of the treatment are referred to as treatment emergent adverse events (TEAEs). An AE can therefore be any unfavorable and unintended sign (for example, an abnormal laboratory finding), symptom, or disease temporally associated with the use of a medicinal product, whether or not considered related to this medicinal product.

A suspected adverse reaction is any AE for which there is a reasonable possibility that the drug caused the AE. 'Reasonable possibility' means there is evidence to suggest a causal relationship between the drug and the AE. A suspected adverse reaction implies a lesser degree of certainty about causality than adverse reaction, which means any AE caused by a drug.

An AE may be:

- A new illness,
- Worsening of a concomitant illness,
- An effect of the study medication including comparator; it could be an abnormal laboratory value as well as a significant shift from baseline within normal range which the Principal Investigator or medical qualified designate considers to be clinically important.

Surgical procedures themselves are not AEs. They are therapeutic measures for conditions that required surgery. The condition for which the surgery is required is an AE, if it occurs or is detected during the study period. Planned surgical measures permitted by the clinical study protocol and the condition(s) leading to these measures are not AEs, if the condition(s) was (were) known before the start of study treatment. In the latter case, the condition should be reported as medical history.

A serious adverse event (SAE) or reaction is any untoward medical occurrence that at any dose:

- Results in death,
- Is life-threatening,
- Requires inpatient hospitalization or prolongation of existing hospitalization,
- Results in persistent or significant disability or incapacity (defined as a substantial disruption of a person's ability to conduct normal life functions),
- Is a congenital anomaly or birth defect,

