12.3 Serious Adverse Event Reporting

Algorithme Pharma will notify any SAE to the sponsor, without regard to causality, within 24 hours after becoming aware of its occurrence.

If, during follow-up, any non-serious AE worsens and eventually meets the criteria for an SAE, that AE should be recorded as a new SAE.

The initial SAE report must be as complete as possible, including details of the current illness and SAE, and an assessment of the causal relationship between the event and the investigational product(s). Information not available at the time of the initial report (eg, an end date for the AE, laboratory values received after the report, or hospital discharge summary) must be documented. All follow-up information must be reported as soon as the relevant info is available.

The notification should be directed to the following sponsor representatives:

PPD

Tel. **PPD**

Fax. **PPD**

Email: **PPD**

An SAE will be considered “unexpected” if the AE is not listed in the investigator brochure or is not listed at the specificity or severity that has been observed; or, if an investigator brochure is not required or available, is not consistent with the risk information described in the general investigational plan or elsewhere in the current application. "Unexpected," as used in this definition, also refers to AEs that are mentioned in the investigator brochure as occurring with a class of drugs or as anticipated from the pharmacological properties of the drug, but are not specifically mentioned as occurring with the particular drug under investigation.

Algorithme Pharma will determine whether any serious unexpected related AE must be reported to the IRB. If so, the event will be reported via fax or email within 15 calendar days of the investigator or staff becoming aware of the event.

The sponsor will determine whether the SAE must be reported in an expedited manner to the appropriate regulatory agencies. If so, Algorithme Pharma Inc, on the behalf of the sponsor will report the event to the appropriate regulatory agencies, and all participating investigators.

During a clinical trial conducted in Canada, it is required to inform Health Canada of any serious, unexpected adverse drug reaction that has occurred inside or outside Canada:

- Where it is neither fatal nor life-threatening, within 15 days after becoming aware of the information;

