10. SAFETY

Adverse Events

An AE is defined as any untoward medical occurrence in a subject administered a medicinal product and which does not necessarily have to have a causal relationship with this treatment. An AE can therefore be any unfavorable and unintended sign (for example, an abnormal laboratory finding), symptom, or disease temporally associated with the use of a medicinal product, whether or not considered related to this medicinal product.

A suspected adverse reaction is any AE for which there is a reasonable possibility that the drug caused the AE. 'Reasonable possibility' means there is evidence to suggest a causal relationship between the drug and the AE. A suspected adverse reaction implies a lesser degree of certainty about causality than adverse reaction, which means any AE caused by a drug.

AEs occurring after the initiation of the treatment are referred to as treatment emergent adverse events (TEAEs).

TEAEs will be assigned to a treatment based on the time of occurrence in relation to the last treatment administered prior to the onset of the TEAE. TEAEs will be assigned using the following rules:

- TEAE will be assigned to the last treatment taken by the subject where the date and time of the last treatment dosing is on or before of the start date and time of the event. Such assignment will be performed irrespective of any washout period between the start and stop dates of the TEAE.
- Any TEAE started after the discharge and during the follow-up period will be assigned to the last treatment that the subject has taken during last period.

As an overall summary of AEs, the following will be presented by treatment and overall:

- Number of reported AEs;
- Number of reported TEAEs;
- Number and percentage of subjects experiencing TEAEs;
- Number and percentage of subjects experiencing a drug-related TEAE (i.e. those with a relationship classified as reasonable possibility)
- Number and percentage of TEAEs by relationship to study treatment (i.e. reasonable possibility, no reasonable possibility);
- Number and percentage of TEAEs by severity;
- Number of reported SAEs (serious adverse events);
- Number and percentage of subjects experiencing SAEs;
- Number and percentage of subjects experiencing drug-related SAEs;
- Number and percentage of TEAEs leading to withdrawal; and
- SAEs with an outcome of death.

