Severe [n(%)]	xx (xx.x)	xx (xx.x)	xx (xx.x)	xx (xx.x)	xx (xx.x)	xx (xx.x)
Life-Threatening [n(%)]	xx (xx.x)	xx (xx.x)	xx (xx.x)	xx (xx.x)	xx (xx.x)	xx (xx.x)

Date: VERSION - YYYY-MM-DD

Data Source: XXXX

Table 14.3.1.5
Summary of Treatment Emergent Adverse Events by System Organ Class, MedDRA Preferred Term and Relationship
To Study Drug
(Safety Population)

SOC MedDRA Preferred Term	Placebo	Lasmiditan 50 mg	Lasmiditan 100 mg	Lasmiditan 200 mg	Alprazolam 1 mg	Overall
Subjects With At Least One TEAE [n(%)]	xx (xx.x)	xx (xx.x)	xx (xx.x)	xx (xx.x)	xx (xx.x)	xx (xx.x)
System Organ Class 1 [n(%)]	xx (xx.x)	xx (xx.x)	xx (xx.x)	xx (xx.x)	xx (xx.x)	xx (xx.x)
MedDRA Term 11 [n(%)]	xx (xx.x)	xx (xx.x)	xx (xx.x)	xx (xx.x)	xx (xx.x)	xx (xx.x)
Reasonable Possibility	xx (xx.x)	xx (xx.x)	xx (xx.x)	xx (xx.x)	xx (xx.x)	xx (xx.x)
NO Reasonable Possibility	xx (xx.x)	xx (xx.x)	xx (xx.x)	xx (xx.x)	xx (xx.x)	xx (xx.x)
MedDRA Term 12 [n(%)]	xx (xx.x)	xx (xx.x)	xx (xx.x)	xx (xx.x)	xx (xx.x)	xx (xx.x)
System Organ Class 2 [n(%)]	xx (xx.x)	xx (xx.x)	xx (xx.x)	xx (xx.x)	xx (xx.x)	xx (xx.x)
MedDRA Term 21 [n(%)]	xx (xx.x)	xx (xx.x)	xx (xx.x)	xx (xx.x)	xx (xx.x)	xx (xx.x)
Reasonable Possibility	xx (xx.x)	xx (xx.x)	xx (xx.x)	xx (xx.x)	xx (xx.x)	xx (xx.x)
NO Reasonable Possibility	xx (xx.x)	xx (xx.x)	xx (xx.x)	xx (xx.x)	xx (xx.x)	xx (xx.x)
MedDRA Term 22 [n(%)]	xx (xx.x)	xx (xx.x)	xx (xx.x)	xx (xx.x)	xx (xx.x)	xx (xx.x)
Etc.	xx (xx.x)	xx (xx.x)	xx (xx.x)	xx (xx.x)	xx (xx.x)	xx (xx.x)

Note(s): Each treatment emergent adverse event is counted only once for each subject under the worst relationship within each System Organ Class and MedDRA Preferred Term.

Date: VERSION - YYYY-MM-DD

Data Source: XXXX

Program Source: XXXXX.sas

Table 14.3.2.1
Listing of Deaths, Other Serious and Significant Adverse Events
(Safety Population)

Subject ID/Gender/ Age	Day Treatment AE #	SOC MedDRA Preferred Term Description of AE	Onset Date Time (Time since Last Dose)	Resolution Date Time (Duration)	I: Maximal Intensity R: Causality Assessment	O: Outcome S: Serious AE D: AE Lead To Discontinuation	Action Taken With Study Treatment / Other Action(s) Taken / Concomitant Given
xxx	xxxxx xxxxx	xxxxxxxxxxxxx xxxxxxxxxxxxx	YYYY-MM-DD/ HH:MM (DD:HH:MM)	YYYY-MM- DD/ HH:MM (DD:HH:MM)	xxxxxxx	xxxxxx	xxxxxxx

Date: VERSION - YYYY-MM-DD

Data Source: XXXX

Program Source: XXXXX.sas

Similar Tables:

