APPENDIX D

LISTING SHELLS

Listing 16.2.1
Listing of Study Disposition

Subject ID/Gender/Age	Sequence	Date of Completion or Discontinuation	Subject Status	Specify	AE #	Date of Death
-----------------------	----------	---------------------------------------	----------------	---------	------	---------------

Date: VERSION - YYYY-MM-DD

Data Source: XXXX

Program Source: XXXXX.sas

Listing 16.2.3
Listing of Analysis Populations

Subject	Safety	PK	Intent-to-treat	Reason if Excluded from one
ID/Gender/Age	Sequence	Population	Population	Population

Date: VERSION - YYYY-MM-DD

Data Source: XXXX

Program Source: XXXXX.sas

Listing 16.2.4.1
Listing of Demographic Characteristics

Subject ID	Sequence	Age	Date of Birth	Gender	Ethnicity	Race	Other Race	Weight at Screening (kg)	Height (cm)	BMI at Screening (kg/m ²)
------------	----------	-----	---------------	--------	-----------	------	------------	--------------------------	-------------	---------------------------------------

Date: VERSION - YYYY-MM-DD

Data Source: XXXX

Program Source: XXXXX.sas

Listing 16.2.4.2
Listing of Screen Failures

Subject ID	Date	Specify Primary Reason
------------	------	------------------------

Date: VERSION - YYYY-MM-DD

Data Source: XXXX

Program Source: XXXXX.sas

Listing 16.2.5.1
Listing of Investigational Product Administration

Subject ID/Gender/Age	Sequence	Visit	Start Date/Time	Treatment	Route	If Any Dosing Specify	Issues,
--------------------------	----------	-------	--------------------	-----------	-------	--------------------------	---------

Date: VERSION - YYYY-MM-DD

Data Source: XXXX

Program Source: XXXXX.sas

Listing 16.2.5.2
Listing of Lasmiditan Plasma Concentrations

Treatment:

Subject	Sequence	Visit	Time Point	Date / Time	Value
---------	----------	-------	------------	-------------	-------

Date: VERSION - YYYY-MM-DD

Data Source: XXXX

Program Source: XXXXX.sas

Listing 16.2.7
Listing of Adverse Events

Subject ID/Gender/Age	Visit Treatment AE #	SOC MedDRA Preferred Term Description of AE	Onset Date Time (Time since Last Dose)	Resolution Date Time (Duration)	I: Maximal Severity R: Causality Assessment	O: Outcome S: Serious AE D: AE Leading To Discontinuation	Action Taken With Study Treatment / Other Action(s) Taken / Concomitant Given
xxx	xxxxx xxxxx	xxxxxxxxxxxxx xxxxxxxxxxxxx xxxxxxxxxxxxx	YYYY-MM-DD/ HH:MM (DD:HH:MM)	YYYY-MM-DD/ HH:MM (DD:HH:MM)	xxxxxxx	xxxxxx	xxxxxxx

Listing 16.2.8.1
Listing of Blood Chemistry

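### The SAP assigns a TEAE by its start time alone, so a non-serious AE that worsens after a later dose is tabulated at its peak grade under the earlier treatment unless sites open a new record

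*SAP*

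**What the plan says.** SAP section 10 and Protocol 12.1 both call an AE treatment emergent if it occurs after treatment has started. For the treatment column, SAP section 10 looks to the last dose given before the event began. Its first rule selects the treatment for which "the date and time of the last treatment dosing is on or before of the start date and time of the event". It then adds: "Such assignment will be performed irrespective of any washout period between the start and stop dates of the TEAE". Start time is the only date used, and the rule expects some events to run past a washout.

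The AE listing (Listing 16.2.7, SAP Appendix D) has one onset, one resolution and one cell for "I: Maximal Severity R: Causality Assessment". The shell for serious and significant events (Table 14.3.2.1, SAP Appendix B) likewise has one "I: Maximal Intensity". Table 14.3.1.4 reports TEAEs by treatment and maximum severity. Table 14.3.1.5 counts each one under its worst relationship.

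The one explicit rule for a recorded AE that gets worse is in Protocol 12.3: "If, during follow-up, any non-serious AE worsens and eventually meets the criteria for an SAE, that AE should be recorded as a new SAE". Neither document says what start time that new record takes.

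**The concern.** In a crossover, the AE tables should show what happened after each treatment. Here the onset fixes the column, while severity and causality are the worst values over the whole life of the event. If an event spans a dose and worsens after it, the two come from different treatments. The treatment that preceded the worsening shows nothing, and an earlier treatment shows the peak grade.

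This bears on the purpose of the trial. Protocol 6.1 gives dizziness and fatigue as the most common AEs of lasmiditan and as the reason for a driving study. AEs are collected from screening (Protocol 12.2). Each check-in, the evening before dosing, includes an AE assessment and a practice drive of about 20 minutes (Protocol 10.2.1). Symptoms recorded shortly before a dose are therefore possible.

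**Working it through.** The plan states no rate or count on this point, so there is no figure to reproduce. I applied the rules to two invented records and then counted predecessors in the sequence table.

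**Record 1.** Sequence 4 is D-E-C-A-B, so placebo (E) falls on Day 7 and lasmiditan 200 mg (C) on Day 14. A mild headache starts at the Day 13 check-in, is still present at the Day 14 dose, and becomes severe but not serious after it.

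- Start time: Day 13. The last dose on or before it is placebo on Day 7, so the event belongs to placebo.
- Severity kept: the maximum, severe.
- Causality kept: a single assessment. If the worsening leads the investigator to judge a drug relationship reasonably possible, that also goes under placebo.

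| Handling | Placebo column | 200 mg column |
|---|---|---|
| One record, SAP rule as written | 1 TEAE, severe | 0 |
| New record at worsening | 1 TEAE, mild | 1 TEAE, severe |

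Placebo has one TEAE either way, and only its grade changes. The 200 mg column loses a TEAE.

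**Record 2.** Mild dizziness starts at the Day -1 practice drive and is severe after the first dose. No dose precedes the start time, so the assignment rule has no treatment to give it, and by onset it is not treatment emergent. It is still counted in the AEs-reported row of Table 14.3.1.1, which the shell fills only under Overall, and it is still in Listing 16.2.7.

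**Sequence table (SAP section 3, Protocol 9.1).** For lasmiditan 200 mg (C):

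| Position of C | Sequences | Count |
|---|---|---|
| Period 1 | 3, 10 | 2 |
| After placebo (E) | 1, 4 | 2 |
| After 100 mg (B) | 2, 5 | 2 |
| After alprazolam (D) | 6, 8 | 2 |
| After 50 mg (A) | 7, 9 | 2 |

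The same count for the other four treatments gives 2 in every cell. With 80 completers allocated equally there are 80 / 10 = 8 per sequence. Each cell is then 2 × 8 = 16 subjects, so each treatment is given to 16 in Period 1 and to 80 − 16 = 64 in Periods 2 to 5.

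Suppose such a case is equally likely in every sequence and its onset follows the immediately preceding dose (or, in Period 1, precedes the first dose). Then 2/10 = 20% of the worsenings after 200 mg are not TEAEs, 20% are tabulated under placebo, and 3 × 20% = 60% under another active treatment. None are tabulated under 200 mg.

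**Number of events.** Subjects affected per treatment = 80 × (share of doses with an ongoing AE) × (share of those AEs that worsen after the dose). The documents give neither share, so the number cannot be computed.

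**The case against.** The strongest reply is that the outcome depends on recording instructions that are not in the documents. One maximal severity per line in a listing shell suggests that a worsening stays in the original record, but does not prove it. Protocol 12.1 also says that an AE may be the worsening of a concomitant illness. A worsening recorded as its own AE would have a post-dose start time, and the existing rule would assign it correctly. This stands as a condition on the point. It does not remove the point, because that wording does not clearly reach an AE already on record, the SAP does not repeat it, and only worsening to serious is expressly given a new record.

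It is also fair that carrying an event across a washout is an ordinary crossover convention. The defect is the missing clause for worsening. And the listing shows onset, resolution and time since last dose, so a careful reader could spot an event that spans a dose. With one severity per event, though, that reader could not see when it worsened.

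A reader might infer more than the documents support:

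- **That the earlier treatment gains events.** It does not. The event began after that treatment and is already its TEAE. Only the severity or relationship grade rises.
- **That a pre-dose event is lost.** It leaves the TEAE tables only.
- **That most cases inflate placebo.** Placebo is the predecessor of any active dose in 2 of 10 sequences, another active treatment in 6 of 10. A narrower drug-placebo contrast also requires worsening to be commoner after active drug, which is plausible but not shown.
- **That the size is known.** Assuming an ongoing AE at 2-5% of doses and worsening in 20-50% of those gives 80 × 0.02 × 0.2 = 0.32 to 80 × 0.05 × 0.5 = 2.0 subjects per treatment. Neither rate has any basis in the documents, so the range is no estimate.

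**Conclusion.** The point holds in a limited form. Applied as written, and if sites keep a worsening within one record, the rule puts the peak grade of a non-serious AE under the wrong treatment and leaves the treatment after which it worsened with no event. An AE with onset before the first dose is not counted as a TEAE at all.

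The sequence table shows that this can affect every treatment alike. The 20% split also rests on the equal-likelihood and onset assumptions stated in the working. The number of events is unknown and probably small: healthy volunteers, single doses, and a washout of at least 5 days mean that few AEs should still be present at the next dose. The affected outputs are descriptive, with no planned test, and the SDLP analysis is untouched. It is still worth correcting, because a single misplaced severe event is visible in columns of about 80 subjects.

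**What to change.** Amend SAP section 10 along these lines:

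> A TEAE is an AE that starts, or increases in severity, after a dose of study drug. An AE that is ongoing at a dose and increases in severity after it is counted as a new TEAE from the time of worsening, at the worsened severity, and is assigned to that dose. The original record keeps its pre-dose severity.

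Instruct sites to open a new AE record, dated at the worsening, whenever an ongoing AE increases in severity, and state that the new record under Protocol 12.3 is dated in the same way. If AE recording has already begun, use onset and resolution times to find events that span a dose and query the time of worsening before database lock.

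The cost is one SAP paragraph, one recording instruction and possibly a few queries. The downside is that a few continuing events will count under two treatments and add to the event totals. A table footnote should say so.

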11.11 Physical Examination

A physical examination will be performed at Screening and Day 35 or EOS.

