13.4.2 Clinical Laboratory

Clinical laboratory values will be summarized by descriptive statistics by dose. Changes from baseline in clinical laboratory values will be summarized by descriptive statistics. All clinical laboratory values outside normal range (including Screening/Visit 1 and EoS/Visit 5 examination) will be listed by dose and subject number, including demographic information and flagging of values.

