13.4.4 Twelve-lead ECG

All ECG endpoints will be listed by dose, subject and time of assessment and summarized by descriptive statistics. Changes from baseline in ECG parameters will be summarized by descriptive statistics by dose.

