26 SCHEDULE OF ACTIVITIES

Study Procedures	Screening (Within 28 Days Prior to 1st Dose) (Visit 1)	Period 1			Period 2			Period 3			Period 4			Period 5			Follow - Up/E OS
		Day- 1 (V2)	Day 1 (V3)	Day 2 (V4)	Day 6 (V5)	Day 7 (V6)	Day 8 (V7)	Day 13 (V8)	Day 14 (V9)	Day 15 (V10)	Day 20 (V11)	Day 21 (V12)	Day 22 (V13)	Day 27 (V14)	Day 28 (V15)	Day 29 (V16)	Day 35 (Visit 17)
Informed consent	X																
Medical/Social history	X																
Subject Eligibility	X	X			X			X				X		X			
Weight/Height ¹ (BMI)	X																X
Drug and alcohol screen	X	X			X			X				X		X			
Serum Pregnancy Test	X	X ⁹			X ⁹			X ⁹				X ⁹		X ⁹			X
Clinical safety labs	X																X ²
Physical examination	X																X
Epworth Sleepiness Scale	X																
Twelve-lead ECG ³	X																X
Vital signs ⁴	X	X	X		X	X		X	X		X	X		X	X		X
Temperature	X																X
Admission to clinic ⁵		X			X			X			X			X			
Discharge from clinic ⁶				X			X			X			X			X	
Study Drug Administration			X			X			X			X			X		
PK sampling ⁷			X			X			X			X			X		
CogScreen SDC Training/Practice	X	X			X			X			X			X			
Driving Sim Training/Practice	X	X			X			X			X			X			
Simulator Sickness Questionnaire	X																
KSS ⁸			X			X			X			X			X		
Self Perceived Questionnaire (safe to drive)			X			X			X			X			X		
CVDA Drive			X			X			X			X			X		

VAS			X			X			X			X			X		
CogScreen SDC Test			X			X			X			X			X		
C-SSRS	X	X			X			X			X			X			X
Adverse event assessment	X	X	X	X	X	X	X	X	X	X	X	X	X	X	X	X	X
Concomitant meds assessment	X	X	X	X	X	X	X	X	X	X	X	X	X	X	X	X	X

¹ Height and BMI will be measured at Screening only.

² Safety labs (hematology, chemistry and urinalysis) at Screening and Day 35 or EOS only.

³ Twelve-lead ECG will be obtained at Screening and Day 35 or EOS only.

⁴ Vital signs will be collected at Screening, CRU check-in on Days -1, 6, 13, 20, and 27, predose and 1.17 hours post dose on Days 1, 7, 14, 21, and 28, and at Follow-up/Day 35 or EOS.

⁵ Subjects will be inpatient on Days -1, 6, 13, 20, and 27.

⁶ Subjects will be discharged approximately 24 hours post-dose.

⁷ Plasma PK samples for lasmiditan levels will be collected at the following time-points: Days 1, 7, 14, 21, and 28 pre-dose (within 30 minutes before dosing) and 2.58 hours (155 minutes -15 to +30 minutes) post dosing.

⁸ KSS is performed before each drive.

⁹ A serum pregnancy test will be performed upon admission to the unit for females of child-bearing potential.

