For all vital signs, raw values, as well as the change from baseline, at each time point will be summarized by treatment, parameter and visit. Vital signs data will also be presented in a listing.

Subject listing of abnormal on-study vital signs values (Out-of-Range – Not Clinically Significant (NCS) or Clinically Significant (CS)) will be provided. Similarly, CS on-study vital signs values (Out-of-Range – CS) will be presented in a second listing.

Electrocardiogram

A triplicate 12-lead ECG will be obtained at time points throughout the study. In some cases, repeat abnormal ECGs may be obtained.

Raw values at each time point, as well as the change from baseline, will be summarized by sequence, parameter and visit and will also be presented in a listing.

A subject listing of abnormal on-study ECG assessments (Abnormal – NCS or Abnormal – CS) will be provided. Similarly, CS on-study ECG assessments (Abnormal – CS) will be presented in a second listing.

Physical Examination Findings

A physical examination will be conducted and results will be presented in a listing.

A subject listing of abnormal on-study physical examination results (Abnormal – NCS or Abnormal – CS) will be provided, including demographic information. Similarly, CS on-study physical examination results (Abnormal – CS) will be presented in a second listing.

Columbia-Suicide Severity Rating Scale (C-SSRS)

The Columbia-Suicide Severity Rating Scale (C-SSRS) is a suicidal ideation rating scale. The scale identifies behaviors and thoughts that are associated with an increased risk of suicidal actions in the future. The C-SSRS will be performed at Screening, on Days -1, 6, 13, 20, and 27, and Day 35 or EOS.

Subjects who answer 'Yes' to any of the questions on the C-SSRS questionnaire will be presented in a listing

Epworth Sleepiness Scale

The Epworth Sleepiness Scale assessment will be performed at Screening and results will be presented in a listing.

Simulator Sickness Questionnaire

A simulator sickness questionnaire will be performed at Screening and results will be presented in a listing.

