12. CHANGES TO PROTOCOL-SPECIFIED ANALYSES

There is no change from the planned analysis described in the protocol.

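### A laboratory, ECG or physical-examination abnormality first recorded as a TEAE at Day 35/EOS is credited to the Period 5 treatment, which the schedule cannot support, and the documents disagree on by-dose laboratory and ECG summaries

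*SAP*

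**What the plan says.** **Timing of assessments.** The footnotes to Protocol Section 26 state "Safety labs (hematology, chemistry and urinalysis) at Screening and Day 35 or EOS only" and "Twelve-lead ECG will be obtained at Screening and Day 35 or EOS only". SAP Appendix A repeats both. Protocol Section 11.11 adds: "A physical examination will be performed at Screening and Day 35 or EOS". The follow-up visit falls 5 to 9 days after the Day 28 dose (Protocol Section 10.4).

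**Attribution of TEAEs.** SAP Section 10 assigns each TEAE to the last treatment dosed before onset and disregards washout. For late events it says: "Any TEAE started after the discharge and during the follow-up period will be assigned to the last treatment that the subject has taken during last" (that is, Period 5). It makes no exception for a finding that nobody was scheduled to look for since Screening. Both documents name an abnormal laboratory finding as an example of an adverse event. The TEAE table shells (Tables 14.3.1.1 to 14.3.1.5) have treatment columns, including placebo.

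**Laboratory and ECG summaries.** Protocol Section 13.4.2 says "Clinical laboratory values will be summarized by descriptive statistics by dose". Its next sentence, on laboratory changes from baseline, does not mention dose. Protocol Section 13.4.4 says "Changes from baseline in ECG parameters will be summarized by descriptive statistics by dose". SAP Section 10 summarises laboratory tests and ECG by sequence. The shells (Tables 14.3.4.3 and 14.3.6.3) have a single Overall column. Physical examination is only listed. SAP Section 12 says: "There is no change from the planned analysis described in the protocol".

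**ECG frequency.** SAP Section 10 also says "A triplicate 12-lead ECG will be obtained at time points throughout the study", which conflicts with its own Appendix A.

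**The concern.** In a crossover, a by-treatment safety column means something only if the event can be placed in time relative to each dose. A symptom with a known onset time can be. A laboratory, ECG or examination finding first seen at Day 35 cannot: it may have arisen after any of five treatments. The SAP rule still gives it a column, and for these events the column shows which drug came last in the randomised sequence.

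At stake is how the TEAE tables are read. They are the main safety output with treatment columns. If a persisting abnormality came from an earlier lasmiditan period, part of it would sit under another dose, alprazolam or placebo, and the contrast with placebo would shrink.

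The second fault depends on no assumption. The protocol promises by-dose laboratory and ECG summaries that the stated schedule cannot supply, and the SAP replaces them twice, differently each time, without declaring it.

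**Working it through.** The plan gives no figure on this point. Its one design figure, power above 90% for SDLP, reproduces: SE = 6 × √(2/80) = 0.949 cm, and Φ(4.4/0.949 − 1.96) = 99.6%. It plays no part below.

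**Step 1: which treatment is last.** The Period 5 letters for sequences 1 to 10 (Protocol Section 9.1, SAP Section 3) are D, E, A, B, C, A, B, C, D, E. Each treatment is last in 2 of 10 sequences, which is 16 of 80 completers (20%).

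**Step 2: limiting case, full persistence.** Suppose one treatment causes an abnormality that always lasts to Day 35 and is recorded as starting then. By Step 1, 20% of cases reach the correct column and 20% reach each of the other four. The documents give no incidence, so assume 5%, 10% or 20% in 80 subjects. That is 4, 8 or 16 cases, hence 0.8, 1.6 or 3.2 per column. The TEAE percentages use all Safety subjects on that treatment (Table 14.3.1.1, note 1), about 80 per column, so each column shows 1%, 2% or 4%.

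**Step 3: decay.** The documents give no persistence figure. Assume the finding fades with half-life h, with dosing on Days 1, 7, 14, 21 and 28 and observation on Day 35. A finding caused in a given period then has weight 0.5^(days since dose / h), with 34, 28, 21, 14 and 7 days since dose. For lasmiditan 200 mg (C), the sequences giving it in each period end as follows:

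- Period 1: A, E
- Period 2: E, A
- Period 3: B, D
- Period 4: D, B
- Period 5: C, C

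For h = 7 the weights are 0.0345, 0.0625, 0.125, 0.25 and 0.5, which sum to 0.972. The correct share is 0.5/0.972 = 51%. The placebo share is (0.0345 + 0.0625)/(2 × 0.972) = 5%. The share still visible is 0.972/5 = 19%.

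| Assumed half-life (days) | Still visible at Day 35 | Of those: correct column | Of those: placebo column |
|---|---|---|---|
| 3.5 | 7% | 75% | 1% |
| 7 | 19% | 51% | 5% |
| 14 | 40% | 35% | 11% |
| 28 | 62% | 27% | 15% |
| 56 | 78% | 24% | 18% |
| no decay | 100% | 20% | 20% |

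The first two result columns are the same for every treatment. The placebo share depends on the dose, because the sequences pair treatments differently. For 50 mg (A), placebo is last after one of the two Period 3 sequences and one of the two Period 4 sequences, so at h = 7 its share is (0.125 + 0.25)/(2 × 0.972) = 19%.

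**Step 4: persistence only from Periods 4 and 5.** For 200 mg, the four relevant sequences (1, 7, 5, 8) end in D, B, C, C. Half are misassigned and none go to placebo. For 50 mg, sequences 4, 10, 3 and 6 end in B, E, A, A. Half are misassigned and one of four goes to placebo.

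**Step 5: wording side by side.**

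| Item | Protocol | SAP text | SAP shell |
|---|---|---|---|
| Laboratory values | by dose (13.4.2) | by sequence | Overall |
| ECG change | by dose (13.4.4) | by sequence | Overall |
| ECG timing | Screening and Day 35/EOS | repeated through the study (Section 10); Screening and Day 35/EOS (Appendix A) | visits as in Appendix A |
| Changes declared | – | none (Section 12) | – |

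**The case against.** The strongest case on the other side is that these are documentary faults with little effect on results.

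- **Reach.** A reader might infer that a drug effect is spread over all columns in the laboratory and ECG output. The documents do not support that. Those shells have no treatment columns, and physical examination is only listed. Misattribution is possible in the TEAE tables alone. This stands.
- **Not every abnormality.** Under Protocol Section 12.1 a laboratory abnormality or shift is listed as an adverse event when the investigator judges it clinically important. Section 11.7 allows extra tests, so a finding may surface earlier. A subject who withdraws has EOS before all five treatments. This stands and limits the number of events; the documents do not let that number be estimated.
- **Size.** A reader might infer a flat profile with no expected difference from placebo. That needs a single-dose effect to last undiminished for up to 34 days, which no document supports. With a short half-life the main problem is missed events, which relabelling cannot recover. This stands.
- **No bias from unrelated findings.** Three lasmiditan columns together receive 60% and placebo 20%, but that is 20% per column, and the shells have no pooled lasmiditan column. This stands.
- **Existing listings.** The listings of abnormal laboratory, ECG and examination results carry the sequence. The AE listing shell shows treatment and time since last dose but not sequence, so the reader of the TEAE tables must combine listings. This stands in part.
- **Cost of relabelling.** Removing Day 35 findings from the treatment columns would also remove genuine Period 5 effects, which are 75% of visible cases at a 3.5-day half-life. This is a fair objection, and reporting counts both ways answers it.

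**Conclusion.** The point holds in a limited form. For completers, the only scheduled post-dose laboratory, ECG and physical-examination result comes after all five treatments. SAP Section 10 turns a TEAE first recorded there into a Period 5 event without saying that the attribution is conventional. The correct column receives between 20% (no decay) and 75% (assumed 3.5-day half-life) of the findings still visible. At assumed half-lives of 14 days or less, 60% or more are no longer visible at all. These ranges rest on assumed persistence, equal allocation to the ten sequences, and onset recorded at the visit.

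The conflict over by-dose, by-sequence and Overall summaries, the undeclared change and the ECG sentence are plain inconsistencies that need no assumption. The primary SDLP analysis is untouched. This is worth correcting because the correction is cheap; it is not a threat to the trial's main conclusion.

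**What to change.** **SAP Section 10**
- Flag TEAEs whose first evidence is a scheduled Day 35/EOS laboratory, ECG or physical-examination result.
- Show them in a separate row labelled as detected at EOS and not attributable to a single treatment.
- Add the full treatment sequence to the AE listing.
- Give the by-treatment TEAE counts with and without the flagged events.
- Keep the last-treatment rule for events with a known onset time.

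**Reconciliation**
- Replace the by-dose wording in Protocol Sections 13.4.2 and 13.4.4 with an overall Screening-to-Day 35 summary, in line with the schedule as written in both documents.
- Align the SAP text with its shells and record the change in SAP Section 12.
- Reconcile the SAP sentence on triplicate ECGs with Protocol Section 26 and SAP Appendix A.

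**Interpretation**
- Base dose-level safety conclusions on adverse events with a known onset and on the vital signs measured in each period (blood pressure and heart rate). Temperature is taken only at Screening and Day 35/EOS.

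**Cost.** SAP wording, one programming flag, one extra table row and a short protocol clarification. No new data are needed. The downside is that a few events carry a flag and the affected counts appear twice.
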